Covariate(s) of interest: For the per protocol analysis, the regression model will adjust for potential confounding from covariate characteristics assessed at baseline and follow-up, which may include:

• Sociodemographic characteristics; sexual behaviors; gender-based violence (GBV); symptoms of common mental disorders; self-esteem; and level of engagement with the intervention.

Statistical analyses:

1) We will compute descriptive statistics to describe the full study population of randomized individuals at baseline and to describe retention over time in both arms of the intervention. We will also summarize reasons for discontinuing PrEP.

- 2) We will compute descriptive statistics for missing data, including the pattern of missingness across visits for both arms of the intervention, and factors associated with missingness. All information from participants with missing data will be examined to determine if any pattern is evident that would account for the missingness.
- 3) Primary analysis: We will conduct an intent-to-treat analysis using a Poisson regression with robust standard errors to assess the effect of the Youth Friendship Bench SA plus SOC intervention compared to SOC services alone on SRQ-20 scores (with reduced symptoms of common mental health disorders defined as SRQ-20 scores < 7) at 12 weeks after randomization. The main effect can be interpreted as the difference in symptoms of common mental health disorders at 12 weeks between the SA plus SOC arm and SOC only arm of the intervention. The effect of the intervention will be estimated as a relative risk (RR) from the Poisson regression model, with treatment arm assigned at first randomization as the only predictor.

Per-protocol analyses: We will also conduct a per-protocol analysis using the same procedures described above but restricting to participants who received full doses of the Youth Friendship Bench SA plus SOC intervention compared to SOC services alone as described above in the *Measures of intervention use* section. Adjustment for covariates of interest will be performed as described above.

Missing data: Multiple imputation (MI) will be used to address missing data issues for covariates and outcomes. Complete case analysis may be used as the primary analysis if the proportions of missing data are below approximately 5%, or if only the dependent variable has missing values and variables not included in the regression analysis but correlated with a variable with missing values and/or related to its missingness are *not* identified. However, these scenarios are unlikely given our previous research in this patient population. Based on statistical convention that bias is likely in analyses with more than 10% missingness, we will use this threshold to determine whether to impute missing outcome data. If the proportions of missing data are very large more than 40% on outcome variables, trial results may only be considered as hypothesis generating results. In the case of multiple imputation, we will use randomly imputed missing values generated from 100 imputations, under the assumption that the data are conditionally missing at random. Following multiple imputation, we will perform a confirmatory factor analysis such that any discrepancies in covariates introduced from imputing will be resolved for the final analysis.

Secondary analysis: We will also assess the effect of the intervention separately on PTSD, depression, and anxiety symptoms. History of post-traumatic stress symptoms will specifically determined by the Posttraumatic Stress Disorder Checklist for DSM-5 (PCL-5) on the study Case Report Forms (CRFs), depressive symptoms by the Patient Health Questionnaire-9 (PHQ-9), and anxiety symptoms by the Generalized Anxiety Disorder questionnaire (GAD-7).

Secondary Analysis 1: To compare the proportion of young South African women who adhere well to PrEP (based on tenofovir [TFV] levels from a urine point-of-care [POC] assay) between those receiving the Youth Friendship Bench SA plus standard-of-care mental health services versus receipt of standard-of-care services alone, after 4 weeks.

Analysis population: South African AGYW participants enrolled and randomized in a 1:1 ratio to either the Youth Friendship Bench SA plus SOC intervention or the SOC services alone arm.

Outcome: proportion of AGYW with PrEP adherence at Week 4, defined as tenofovir (TFV) concentrations ≥1500 ng/mL in urine measured using a urine POC assay.

Predictor(s) of interest: Randomized intervention arm, either the Youth Friendship Bench SA plus SOC or SOC services alone groups.

Statistical analyses:

- 1) We will compute descriptive statistics to describe the full study population of randomized individuals at baseline and to describe retention over time in both arms of the intervention. We will also summarize reasons for discontinuing PrEP.
- 2) We will compute descriptive statistics for missing data, including the pattern of missingness across visits for both arms of the intervention, and factors associated with missingness. All information from participants with missing data will be examined to determine if any pattern is evident that would account for the missingness.
- 3) Primary analysis: We will conduct an intent-to-treat analysis using a Poisson regression with robust standard errors to assess the effect of the Youth Friendship Bench SA plus SOC intervention compared to SOC services alone on TFV levels measured in urine (with PrEP adherence defined as TFV ≥1500 ng/mL) at 4 weeks after randomization. The main effect can be interpreted as the difference in PrEP adherence at 4 weeks between the SA plus SOC arm and SOC only arm of the intervention. The effect of the intervention will be estimated as a relative risk (RR) from the Poisson regression model, with treatment arm assigned at first randomization as the only predictor.

Secondary Analysis 2: To assess the correlates of PrEP adherence, after adjusting for study arm, including sociodemographic factors and psychosocial and behavioral characteristics.

Analysis population: South African AGYW participants enrolled and randomized in a 1:1 ratio to either the Youth Friendship Bench SA plus SOC intervention or the SOC services alone arm.

Outcome: correlates of PrEP adherence at 12 weeks, adjusted for study arm

Predictor(s) of interest: Randomized intervention arm, either the Youth Friendship Bench SA plus SOC or SOC services alone groups; and covariates described below.

- Covariate characteristics assessed at baseline and follow-up may include Sociodemographic characteristics; sexual behaviors; gender-based violence (GBV); symptoms of common mental disorders; self-esteem; and level of engagement with the intervention.
- Other covariates will be selected via the processes described below.

Covariate selection process for multivariable models: We will use a combination of consulting previous research, univariate analyses, and forward stepwise selection to determine which sociodemographic factors and psychosocial and behavioral characteristics will be included in our multivariable models:

 We will first determine which variables to include based on pre-existing research and theories. We will consult pre-existing research on variables associated with PrEP adherence to narrow down our list of variables to include in our secondary analysis. We will also create a rough theoretical "model" of the relationship between associated variables and our outcome of PrEP adherence to ensure there are no temporality concerns and to help us understand which variables may be mediators/moderators of others.

- 2) Before building our model, we will conduct univariate chi-squared tests to assess the relationship between each covariate selected from the previously defined step and PrEP adherence. Based on this test, variables with a p-value greater than alpha-level of 0.05 will be included in our multivariable model.
- 3) After selecting our covariates, we will build our model using forward stepwise selection. Broadly, forward selection begins with a null model and adds one independent variable at a time, starting with the variable whose inclusion gives the most statistically significant improvement of the fit by looking at the Akaike Information Criterion (AIC) and Bayesian Information Criterion (BIC) model fit statistics. AIC penalizes the number of parameters to avoid overfitting. In a Poisson model, a lower AIC indicates a better model fit. BIC is similar to AIC but has greater penalties for more complex models. Similarly, a lower BIC indicates a better model fit. We will repeat this process until no additions significantly improve the model fit. The final model's AIC and BIC will be presented in the table.

Statistical analyses:

- We will conduct an intent-to-treat analysis using a Poisson regression with robust standard errors to assess the association of selected covariates on TFV levels measured in urine (with PrEP adherence defined as TFV ³1500 ng/mL) at 12 weeks, adjusting for study arm. The effect of each covariate on PrEP adherence will be estimated as a relative risk (RR) from the Poisson regression model.
- 2) We will also conduct a per-protocol analysis using the same procedures described above, but only amongst participants who received full doses of the Youth Friendship Bench SA plus SOC intervention or SOC only.

Secondary Analysis 3: To assess the correlates of symptoms of common mental disorders, after adjusting for study arm, including sociodemographic factors and psychosocial and behavioral characteristics.

Analysis population: South African AGYW participants enrolled and randomized in a 1:1 ratio to either the Youth Friendship Bench SA plus SOC intervention or the SOC services alone arm.

Outcome: correlates of common mental disorder symptoms at 12 weeks, adjusted for study arm [categorical SRQ variable; categories: >7, <7]

Predictor(s) of interest: Randomized intervention arm, either the Youth Friendship Bench SA plus SOC or SOC services alone groups; and covariates described below.

• Covariate characteristics assessed at baseline and follow-up may include Sociodemographic characteristics; sexual behaviors; gender-based violence (GBV); self-esteem; and level of engagement with the intervention

Covariate selection process for multivariable models: We will use the same process described above using separate theoretical guidelines and univariable analyses for variable selection.

Statistical analyses:

1) We will conduct an intent-to-treat analysis using a Poisson regression with robust standard errors to assess the association of selected covariates on reduced symptoms of common mental disorders at 12 weeks, adjusting for study arm. The effect of each

covariate on symptoms of common mental disorders will be estimated as a relative risk (RR) from the Poisson regression model.

2) We will also conduct a per-protocol analysis using the same procedures described above, but only amongst participants who received full doses of the Youth Friendship Bench SA plus SOC intervention or SOC only.

Secondary Analysis 4: To qualitatively explore the acceptability, feasibility, and appropriateness of the Youth Friendship Bench SA intervention and the POC TFV urine assay.

- Qualitative factors that influence acceptability, feasibility, and appropriateness of the Youth Friendship Bench SA intervention
- SAEs (including events that result in death, are life-threatening, require inpatient hospitalization or prolongation of existing hospitalization, and/or result in persistent or significant disability/incapacity) and adverse events of special interest (reports of self-harm or self-injury).
- We will analyze qualitative data (in-depth interviews, clinic observation field notes) using an inductive and deductive coding approach and will use descriptive statistics to summarize quantitative data on intervention acceptability, feasibility, and appropriateness and SAEs and AESIs.

Secondary Analysis 5: To monitor and describe the occurrence of serious adverse events over the study (defined as those events that result in death, are life-threatening, require inpatient hospitalization or prolongation of existing hospitalization, and/or result in persistent or significant disability/incapacity) plus adverse events of special interest (reports of self-harm or self-injury).

Statistical analyses:

1) We will compute descriptive statistics to describe the occurrence of serious adverse events and adverse events of special interest. For the full study population, we will compute means, standard deviations, medians, and inter-quartile ranges for each of the adverse events that may occur. Chi-squared tests will be used to assess differences in adverse study events across meaningful groupings, such as between study arms.

Exploratory Objective 1: To explore mediators and moderators of the Youth Friendship Bench SA intervention effect on PrEP adherence.

- Mediators and moderators of the Youth Friendship Bench SA intervention effect on PrEP adherence at 12 weeks
- Covariate characteristics assessed at baseline and follow-up may include Sociodemographic characteristics; sexual behaviors; gender-based violence (GBV); symptoms of common mental disorders; self-esteem; intervention acceptability, feasibility, and appropriateness; and level of engagement with the intervention.

Exploratory Objective 2: To explore mediators and moderators of the Youth Friendship Bench SA intervention effect on symptoms of common mental disorders.

• Mediators and moderators of the Youth Friendship Bench SA intervention effect on symptoms of common mental disorders at 12 weeks

 Covariate characteristics assessed at baseline and follow-up may include Sociodemographic characteristics; sexual behaviors; gender-based violence (GBV); symptoms of common mental disorders; self-esteem; self-reported PrEP adherence; intervention acceptability, feasibility, and appropriateness; and level of engagement with the intervention.

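### Forward selection of correlates uses AIC and BIC from a Poisson likelihood on a yes/no outcome, so entry is too strict and the selected set can depend on how SRQ-20 is coded

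*SAP*

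**What the plan says.** The SAP's covariate selection process for Secondary Analysis 2 has three steps: a theory-based shortlist, a univariate chi-squared screen, and forward stepwise selection. On the third, the SAP writes "Broadly, forward selection begins with a null model and adds one independent variable at a time", with fit judged by AIC and BIC, and explains that "In a Poisson model, a lower AIC indicates a better model fit". The stopping rule is "We will repeat this process until no additions significantly improve the model fit". It gives no cut-off and does not say what happens if AIC and BIC disagree.

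The model is fitted "using a Poisson regression with robust standard errors to assess the association of selected covariates on TFV levels measured in urine". A woman counts as adherent at a concentration of 1500 ng/mL or more, so the outcome is binary. It is reported "at 12 weeks, adjusting for study arm".

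Secondary Analysis 3 (common mental disorder symptoms) adopts the procedure: "We will use the same process described above using separate theoretical guidelines and univariable analyses for variable selection". Its objective speaks of symptoms, its outcome line lists categories above 7 and below 7 (a score of exactly 7 falls in neither), and its analysis line models reduced symptoms.

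The step 2 screen reads "variables with a p-value greater than alpha-level of 0.05 will be included in our multivariable model".

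Protocol section 11.4.3 and the SAP's table shells (Appendix, Tables 4 and 5) give logistic regression for these same two analyses, and the shells report odds ratios.

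**The concern.** Robust Poisson regression is a sound way to estimate a relative risk for a binary outcome, because the sandwich variance corrects the standard errors of a working model. AIC and BIC do not use that variance. They use the working log-likelihood, which takes the outcome variance to be p when it is p(1-p). The gain in fit from adding a covariate is understated, while the AIC and BIC penalties stay the same.

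Two things follow. Real correlates are missed more often than the nominal criteria imply. The size of the error also depends on which outcome category is called the event, so the same data can give different selected sets when SRQ-20 is coded as below 7 or as 7 and above. Secondary Analysis 3 does not fix that direction. Two named secondary objectives are affected; the co-primary comparisons are not.

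**Working it through.** The plan states no figure for this procedure, so there is none to reproduce.

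**Inputs from the SAP (Sample size; Power calculations)**
- 110 randomised, 85-90% retained: 110 × 0.85 = 93.5 and 110 × 0.90 = 99. I use n = 97, within that range.
- Adherence 40% in control plus 20 points: 40% and 60%, pooled 50%.
- Symptoms 50% in control and a 25-point difference, taken as a reduction: SRQ-20 below 7 in 50% and 75%, pooled 62.5%. Coded as symptoms, pooled 37.5%. The correlate models pool both arms, so the pooled rate is the relevant one.

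**Formula.** For one added binary covariate with level sizes n_k and observed rates p_k, the Poisson likelihood-ratio statistic is approximately Σ n_k (p_k - p)² / p. The Bernoulli statistic is approximately Σ n_k (p_k - p)² / [p(1-p)], which is chi-square(1) when the covariate has no effect. The Poisson statistic is therefore about (1-p) times chi-square(1). AIC requires a gain above 2 and BIC a gain above ln(97) = 4.575, so the effective chi-square cut-offs are 2/(1-p) and 4.575/(1-p).

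| Likelihood, event rate | AIC cut-off | AIC entry p | BIC cut-off | BIC entry p |
|---|---|---|---|---|
| Bernoulli, any rate | 2 | 0.157 | 4.575 | 0.032 |
| Poisson, 37.5% (symptoms) | 3.20 | 0.074 | 7.32 | 0.007 |
| Poisson, 50% (adherence) | 4.00 | 0.046 | 9.15 | 0.0025 |
| Poisson, 62.5% (SRQ-20 below 7) | 5.33 | 0.021 | 12.20 | 0.0005 |

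**Chance of keeping a true correlate.** Assumed, not from the documents: one binary covariate split about evenly (49 women at the higher-rate level, 48 at the lower) and a 20-point difference. Probabilities are exact, summed over all binomial outcomes, with no prior screen.

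| Rates | Criterion | Poisson | Poisson, coding reversed | Bernoulli | Two codings disagree |
|---|---|---|---|---|---|
| 72.5% vs 52.5% (pooled 62.5%) | AIC | 40% | 61% | 73% | 21% |
| | BIC | 8% | 26% | 49% | 19% |
| 60% vs 40% (pooled 50%) | AIC | 49% | 50% | 71% | 6% |
| | BIC | 15% | 15% | 47% | 5% |

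**Adding the step 2 screen**
- Read as p<0.05. At 72.5% vs 52.5%, the covariate passes both steps in 40% (Poisson AIC) against 54% (Bernoulli AIC); with BIC, 8% against 49%. At 60% vs 40%, AIC gives 48% against 49%; with BIC, 15% against 47%.
- Read literally, as p>0.05. At 72.5% vs 52.5%, Poisson AIC keeps essentially none and Bernoulli AIC 19%. At 60% vs 40%, the figures are about 1% and 23%. BIC keeps essentially none under either likelihood.

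**Study arm.** A 1,000-run forward-selection simulation (n = 96, five binary covariates, two of them true with 20-point differences, arm effect 20 points; all assumed) gave the share of true correlates kept without arm and with arm forced in: Poisson AIC 48.0% and 47.2%, Poisson BIC 14.0% and 13.9%, logistic AIC 71.8% and 72.8%.

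**The case against.** **The univariate screen already does most of the filtering.** This stands in part. If step 2 was meant to pass p<0.05, Poisson AIC at 50% events adds almost no further loss. At 62.5% its entry level of 0.021 is tighter than the screen, and the BIC loss remains at both rates. If step 2 is applied as printed, the screen dominates and changing the likelihood alone does not rescue the analysis.

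**The protocol and table shells say logistic.** Under a logistic likelihood the AIC/BIC and coding problems disappear. That does not clear the SAP text, which specifies Poisson for selection and estimation. It is a contradiction to resolve, and it points to the same repair.

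**Study arm.** A reader might infer from "forward selection begins with a null model and adds one independent variable at a time" that arm is left out, that the final model may be unadjusted, and that this is why correlates are lost. The documents do not support that. The sentence is a general description of forward selection, arm is listed among the predictors of interest, and both reported models adjust for it. The SAP only omits to say whether arm is held in during selection. Arm is randomised, and leaving it out changed retention of true correlates by about one point. Level of engagement, which is tied to arm, was not simulated.

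**Event rate.** A reader might also apply 75% as the SRQ-20 rate, which gives an AIC entry level of 0.005. That is the intervention-arm target, not the pooled rate, and it overstates the problem.

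**Importance.** These analyses are non-confirmatory. This is true and limits the weight of the point.

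**Conclusion.** The selection rule as written is wrong for a binary outcome. Entry is too strict by a factor of about 1/(1-p): 2 at the planned pooled adherence rate and 2.7 at the planned pooled rate of SRQ-20 below 7. True correlates are missed more often, not always. For the assumed 20-point correlate at 62.5% events, retention falls from 73% to 40% with AIC and from 49% to 8% with BIC. The two SRQ-20 codings would disagree about it in roughly one trial in five. At 50% events, coding matters little.

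The entry levels rest on the SAP's planning rates and a large-sample approximation. The retention figures also rest on the assumed covariate split and effect. The AIC part depends on how step 2 is read; the BIC loss persists if step 2 means p<0.05. Handling of study arm during selection is an omission in wording and does not contribute to the loss. The point concerns Secondary Analyses 2 and 3 only, and is worth correcting before they are run.

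**What to change.** 1. In step 3, select on one Bernoulli (logistic) criterion, either AIC or BIC, with its stopping rule stated, and keep study arm in every candidate model.
2. In step 2, correct the direction of the p-value rule.
3. In Secondary Analysis 3, define the outcome as SRQ-20 below 7 versus 7 or above, name which is the event, and apply the same selection procedure.
4. Reconcile the SAP text (Poisson, relative risks) with protocol section 11.4.3 and SAP Tables 4 and 5 (logistic, odds ratios). Relative risks may still be estimated by robust Poisson on the selected set.

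The cost is SAP wording and a few lines of code, with no change to data collection. The trade-off is more false-positive correlates. In the simulation with arm forced in and no screen, a null covariate was kept in 17.8% of cases with logistic AIC against 3.9% with Poisson AIC, and in 3.9% against 0.2% with BIC. A p<0.05 screen ahead of selection would hold the rate to about 5% per null covariate.

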Statistical Analysis Plan

Title: Friendship Bench Mental Health Intervention for Adolescent Girls and Young Women in South African PrEP Delivery Settings

NCT05664490

Date Created: 15 January 2024 **Last Updated:** 29 July 2024 Drafted by: [name] MPH; [name]; [name]

Statistical Team

University of California San Francisco, San Francisco, USA

University of the Witwatersrand, Johannesburg, South Africa

Table of Contents

Background and Rationale	. 3
Study Objectives and Hypothesis	. 3
Study Design	. 4
Schema	. 5
Overview of Study Design	. 7
Sample size and power calculations	. 8
Data Analysis	. 8

Background and Rationale

The purpose of this study is to adapt and test the Friendship Bench for South African adolescent girls and young women (AGYW) attending PrEP services, using a hybrid effectiveness-implementation trial.

The Friendship Bench is an ideal starting point for treating mild-to-moderate symptoms of common mental disorders among AGYW in PrEP delivery settings, given that it was designed for and tested in a similar African context. The proposed study will test and optimize the Friendship Bench for AGYW with mental health needs in South African/PrEP programs ("Youth Friendship Bench SA").

Study Objectives and Hypotheses

The co-primary objectives of this study are:

- To compare the proportion of young South African women who adhere well to PrEP (based on tenofovir [TFV] levels from a urine point-of-care [POC] assay) between those receiving the Youth Friendship Bench SA plus standard-of-care (SOC) mental health services versus receipt of standard-of-care services alone, after 3 months
- To compare the proportion of young South African women with reduced symptoms of common mental disorders (based on SRQ-20 score) between those receiving the Youth Friendship Bench SA plus standard-of-care mental health services versus receiving standard-of-care services alone, after 3 months

The secondary objectives of this study are:

- To compare the proportion of young South African women who adhere well to PrEP (based on tenofovir [TFV] levels from a urine point-of-care [POC] assay) between those Youth Friendship Bench SA, Version 1.030August 202222receiving the Youth Friendship Bench SA plus standard-of-care mental health services versus receipt of standard-of-care services alone, after 4 weeks.
- To assess the correlates of PrEP adherence, after adjusting for study arm, including sociodemographic factors and psychosocial and behavioral characteristics.

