Appendix – Table shells for primary and secondary analyses

Table 1: Co-Primary Analysis 1

Associations between Youth Friendship Bench SA intervention and PrEP adherence at Week 12, assessed via univariate and multivariable Poisson regression models with robust standard errors

Exposure group	Urine TFV ≥1500 ng/mL						
	ITT analysis (n = XX)			Per-protocol analysis (n = XX)			
	n (%)	RR (95% CI)	p -value	n (%)	aRR (95% CI)	p -value	
Intervention arm							

Standard-of-care

Table 2: Co-Primary Analysis 2

Associations between Youth Friendship Bench SA intervention and symptoms of common mental health disorders at Week 12, assessed via univariate and multivariable Poisson regression models with robust standard errors

Exposure group	SRQ-20 score < 7						
	ITT analysis (n = XX)			Per-protocol analysis (n = XX)			
	n (%)	RR (95% CI)	p-value	n (%)	aRR (95% CI)	p -value	
Intervention arm							

Standard-of-care

Table 3: Secondary Analysis 1

Associations between Youth Friendship Bench SA intervention and PrEP adherence at Week 4, assessed via univariate and multivariable Poisson regression models with robust standard errors

	Urine TFV ≥1500 ng/mL						
Exposure group	ITT analysis (n = XX)			Per-protocol analysis (n = XX)			
	n (%)	RR (95% CI)	p -value	n (%)	aRR (95% CI)	p -value	
Intervention arm							
Standard-of-care							

Table 4: Secondary Analysis 2

Correlates of PrEP adherence at Week 12 assessed via univariate and multivariable logistic regression models

Characteristic	Unadjusted model		Adjusted for study arm		
	OR (95% CI)	p -value	aOR (95% CI)	p -value	
Sexual behaviors					
Gender-based violence					
Symptoms of common mental disorders					
Self-esteem					
Level of engagement with intervention					

Table 5: Secondary Analysis 3

Correlates of symptoms of common mental health disorders at Week 12 assessed via univariate and multivariable logistic regression models

Characteristic	Unadjusted model		Adjusted for study arm		
	OR (95% CI) p -value		aOR (95% CI)	p -value	
Sexual behaviors					
Gender-based violence					
Symptoms of common mental disorders					
Self-esteem					
Level of engagement with intervention					

References

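### The SAP does not say whether the adjusted column of Tables 4 and 5 holds each factor plus study arm or the final stepwise model, and the stepwise procedure cannot fill those tables

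*SAP*

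**What the plan says.** **SAP text, Secondary Analysis 2.** The covariate section says: "We will use a combination of consulting previous research, univariate analyses, and forward stepwise selection to determine which sociodemographic factors" and related characteristics enter. Candidates are narrowed by theory, screened by chi-squared tests, then added one at a time on AIC and BIC: "We will repeat this process until no additions significantly improve the model fit". The reported model is a Poisson regression "to assess the association of selected covariates on TFV levels measured in urine", with arm included, and the final model's fit statistics are to appear in the table. Secondary Analysis 3 follows suit: "We will use the same process described above using separate theoretical guidelines and univariable analyses for variable selection".

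**SAP objective and outcome line.** The objective is "To assess the correlates of PrEP adherence, after adjusting for study arm, including sociodemographic factors and psychosocial and behavioral characteristics". The outcome line reads "correlates of PrEP adherence at 12 weeks, adjusted for study arm".

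**SAP Appendix, Tables 4 and 5.** Five factor rows are listed: sexual behaviors, gender-based violence (GBV), symptoms, self-esteem and engagement. Each has an unadjusted cell and a cell headed "Adjusted for study arm". There is no sociodemographic row and no AIC or BIC cell. The titles describe the models as univariate and multivariable.

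**Protocol 11.4.3.** Correlates are assessed by logistic regression on the covariates listed under the endpoints (11.2.3). No selection step is mentioned.

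**The concern.** One factor plus arm and a mutually adjusted selected model answer different questions. Arm is randomized, so it is independent of baseline factors. Adjusting a baseline factor for arm therefore nearly reproduces its unadjusted estimate and removes no confounding by other factors. The selected model conditions each retained factor on the others and gives nothing for the rest.

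The protocol's background (5.1) links GBV and other stressors to symptoms, and symptoms to adherence. In that structure the two quantities separate: a factor acting through symptoms has a total association that mutual adjustment for symptoms removes.

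Two stated secondary objectives depend on this column. As written, the choice of model can be made after both sets of results have been seen, and a reader of the finished table could not tell a total association from a mutually adjusted one.

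**Working it through.** The plan gives no figure to reproduce here. The check compares the texts and then illustrates the consequence.

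**1. Which model fills the adjusted column?**

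| Feature | Points to factor plus arm | Points to stepwise model |
|---|---|---|
| Column header names only arm | yes | |
| Fixed row for each listed factor | yes | |
| No AIC or BIC cell in the shells | yes | |
| Protocol 11.4.3: listed covariates, no selection | yes | |
| SAP text: only covariates that survive selection | | yes |
| SAP text: AIC and BIC in the table | | yes |
| Objectives and outcome line | compatible | compatible |
| Table titles (multivariable) | compatible | compatible |

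One factor plus arm is also a multivariable model, so the titles do not settle the matter. Nothing says what to print for an unselected factor.

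**2. Size of the data.** The SAP randomizes 110 and expects 85-90% retention: 0.85 × 110 = 93.5 and 0.90 × 110 = 99. The illustrations use 96 (96/110 = 87%). The power section assumes 40% adherence under standard of care and a 20% difference. Read as percentage points, that averages (40 + 60)/2 = 50%, or 0.50 × 96 = 48 events. For symptoms, 50% and a 25-point difference average (50 + 25)/2 = 37.5%, or 36 women in the smaller outcome group.

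**3. What forward selection does at this size.** Assumptions from outside the documents: GBV in 40%; GBV and low self-esteem each raise the odds of symptoms by a factor of 2 to 4; GBV has no direct effect on adherence; about 50% are adherent. The symptoms RR of 0.75 corresponds to the protocol's 25% lower adherence with symptoms.

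- Selection by AIC left every listed row empty in about 24-56% of simulated trials. Runs using the Poisson likelihood for selection gave 61-65%.
- With selection by AIC and no screen, the symptoms RR averaged about 0.62 in trials where it was selected. With a screen keeping p < 0.05 it averaged about 0.59. On the log scale, ln 0.62 / ln 0.75 = 0.478/0.288 = 1.66, an exaggeration of about two-thirds.
- A pre-specified model with all covariates plus arm filled every row, averaged about 0.74 and had 94-96% interval coverage.

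The inflation figures do not cover the screen as literally written, which keeps p > 0.05.

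**4. Would GBV be a correlate on one reading and absent on the other?** Under the same assumptions the plus-arm GBV RR is 0.95 to 0.89. With 0.4 × 96 = 38.4 exposed and 57.6 unexposed at 50% adherence, SE(log RR) = √(1/38.4 + 1/57.6) = 0.21. Then z = 0.051/0.21 to 0.117/0.21, or about 0.25 to 0.56, and the chance of p < 0.05 is about 6-9%. GBV was significant with arm only, yet missing from the stepwise model, in about 0.2-5% of trials.

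A separate simulation assumed 94 or 110 women, correlated factors and mostly stronger effects (GBV RR down to 0.5), with a p < 0.05 screen. It gave about 2-25% with AIC and 4-44% with BIC. With the screen as literally written it gave about 4-87%, but that range is driven by the direction of the screen, which is a separate point. A spread this wide shows the result depends on the assumptions.

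**The case against.** The best defence is that this is a drafting gap, not a contradiction. A reader might infer that the SAP defines the adjusted estimate twice, once as stepwise and once as adjusted for arm alone. The documents do not support that. No passage says arm alone. The objective, "To assess the correlates of PrEP adherence, after adjusting for study arm", fits any model that contains arm, and the stepwise text describes its own model as adjusting for arm. The objectives are therefore not evidence of a second definition.

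The shells also look like a template. Table 5 keeps symptoms as a correlate of symptoms, although the covariate list for Secondary Analysis 3 omits it, so the fixed rows may not reflect a deliberate choice. Step 1 does call for a theoretical model of mediators and moderators before selection. A reader might also infer that GBV will often be a correlate in one version and vanish in the other. Under the mediated scenario that happened in only about 0.2-5% of trials.

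All of this stands, and it limits the claim to an undefined column. It does not remove the problem: theory in step 1 does not say what the column contains, and however the shells arose, the described procedure cannot fill them.

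**Conclusion.** The point holds as an unresolved specification. The SAP text points to the final stepwise model; the header, fixed rows, missing fit-statistic cell and Protocol 11.4.3 point to each factor plus arm. No sentence decides between them. The mismatch itself is read directly from the documents and needs no assumption.

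The consequences of stepwise selection (blank rows, and retained estimates exaggerated from 0.75 to about 0.62) are illustrations at about 96 women under the assumptions above. None of the simulated percentages should be read as the rate at which the trial's conclusions would conflict.

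The matter is confined to Secondary Analyses 2 and 3 and leaves both co-primary comparisons untouched. It should still be settled before the outcome data are examined. The Poisson-versus-logistic mismatch and the direction of the p-value screen are separate points; correcting either would leave this one open.

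**What to change.** Align the text of Secondary Analyses 2 and 3 with Tables 4 and 5:

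1. Drop data-driven forward selection. Fix in advance a short covariate list from the theory step, and add the sociodemographic rows that the objectives call for.
2. For every listed factor report three labelled estimates: unadjusted; plus study arm; and mutually adjusted (all pre-specified covariates plus arm).
3. Report follow-up factors such as level of engagement separately, because they are not baseline factors.
4. Remove the sentence promising the final model's AIC and BIC.

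Conclusions need not rest only on the plus-arm column; it is enough that each column is labelled for what it estimates. Stating which model fills the column and what is shown for unselected factors would be the bare minimum, but would leave the blank rows and the exaggerated estimates.

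The cost is SAP wording and one extra table column, with no new data. The downside is somewhat wider intervals than a selected model gives. With roughly 48 events, five single-term factors plus arm already leave 48/6 = 8 events per term, so the list must stay short.
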